## 2.5 Statistical Interim Analyses and Stopping Guidance

There will be no interim analyses in this trial due to the short duration for each participant and relatively small sample size.

## 2.6 Timing of Main Analysis

The main analysis is planned when all participants have concluded  $84 \pm 7$  days of treatment, all data up to 84 days have been entered, verified and validated and the primary database has been locked.

### 3 Trial Population

#### 3.1 Screening Data, Eligibility and Recruitment

The total number of screened patients and reasons for not entering the trial will be summarised and tabulated.

A CONSORT flow diagram will be used to summarise the number of patients who were:

- assessed for eligibility at screening
- eligible at screening
- ineligible at screening\*
- eligible and randomised
- eligible but not randomised\*
- received the randomised allocation
- did not receive the randomised allocation\*
- lost to follow-up\*
- discontinued the intervention\*
- randomised and included in the primary analysis
- randomised and excluded from the primary analysis\*

\*Reasons will be provided.

##### **Inclusion criteria:**

The following condition must apply to the prospective patient at screening prior to receiving study agent:

- Clinically established diagnosis of idiopathic PD according to the MDS criteria.
- 123I-Ioflupane dopamine transporter imaging (DAT-scan) or 18-F-FDOPA positron emission tomography (18F-FDOPA PET) confirming nigrostriatal degeneration.
- Hoehn and Yahr score < 4 at enrollment.
- Age ≥ 40 years at time of enrollment.
- Able to undergo lumbar puncture.
- Able to undergo MRI.

##### **Exclusion criteria:**

The participant cannot have any of the following prior to receiving study agent:

- Dementia or other neurodegenerative disorder at baseline visit.
- Diagnosed with atypical parkinsonism (PSP, MSA, CBD) or vascular parkinsonism.
- Any psychiatric disorder that would interfere with compliance in the study.
- Metabolic, neoplastic, or other physically or mentally debilitating disorder at baseline visit.
- Use of high dose vitamin B3 supplementation within 30 days of enrollment.

## 3.2 Baseline Patient Characteristics

The patient demographics and baseline characteristics to be summarized include:

- Age (in years).
- Sex (assigned according to electronic patient records).
- Time since PD diagnosis at baseline (in years).
- Weight (in kilograms).
- Height (in centimeters).
- BMI (in kg/m^2).
- Smoking status (Current/Previously/Never, number of pack years (0 - 10 years, > 10 years)).
- Subjective symptom duration of PD (in months).
- Anamnestic RBD (Yes/No).
- Duration of RBD at baseline (in years).
- Anamnestic loss of smell (Yes/No).
- Duration of loss of smell at baseline (in years).
- MDS-UPDRS total score and subsections I-IV.
- MDS-NMS score.
- MoCA score.
- Modified GIDS-PD score.
- Total EQ-ED-5L score.
- EQ-ED-5L subsection EQ VAS score.
- Hoehn and Yahr score.
- B-SIT (Sensonics International, Haddon Heights, NJ, USA) score for subset where available.

Patient demographics and baseline characteristics will be summarized by randomized treatment arm and overall using descriptive statistics (N, mean, standard deviation) for continuous variables, and number and percentages of patients for categorical variables. No formal statistical analysis will be performed between groups as participants were randomized during the trial.

## 3.3 Withdrawal/Follow-up

The status of eligible and randomised patients at trial end will be tabulated by treatment group according to

- completed intervention and assessments
- completed assessments but not intervention
- withdrew consent
- lost to follow-up

## 3.4 Adherence and Protocol Deviations

### 3.4.1 Adherence to Allocated Treatment

Compliance is assessed based on the percentage of subjects who have taken the scheduled number of pills. It is defined as:

% compliance = (number of capsules taken / number of capsules supposed to have been taken) x 100%.

The number of capsules supposed to have been taken will be calculated as the duration of treatment (end of study medication – start of study medication) multiplied by 12 per dispensation of study medication. In this study 6 capsules are taken in the morning and 6 capsules in the evening.

The mean  $\pm$  SD of study drug compliance over the whole study period and between individual visits will be presented in a table by treatment group.

### **3.4.2 Protocol Deviations**

The following are pre-defined major protocol deviations regarded to affect the efficacy of the intervention:

- Entering the trial when the eligibility criteria should have prevented trial entry.
- Discontinuation of intervention prior to  $84 \pm 7$  days.
- Major change in concomitant anti-Parkinson medication.
- Received or used other intervention than allocated.
- Adherence to allocated treatment below 85%.
- Visit date interval larger than  $28 \pm 7$  days between individual visits (i.e.: V1 and V2, V2 and V3, and V3 and V4).
- Visit date interval larger than  $84 \pm 7$  days from V1 to V4.
- Not fasting before neuroimaging.

Protocol deviations are classified prior to unblinding of treatment. The number (and percentage) of patients with major and minor protocol deviations will be summarised by treatment group with details of type of deviation provided. The patients that are included in the FAS analysis data set (see point 3.5 below) will be used as the denominator to calculate the percentages. No formal statistical testing will be undertaken.

## **3.5 Analysis Populations**

The Full Analysis Set (FAS) will be performed using the intention to treat population, defined as all patients randomly assigned to a treatment group and attended the baseline visit.

The Safety Analysis Set will include all patients having received at least one study treatment infusion after randomisation.

The Per Protocol Analysis Set (PPS) will include all randomised patients meeting the study eligibility criteria and with no major protocol deviations affecting the treatment efficacy.

## 4 Endpoint Definitions

### 4.1 General Definitions and Derived Variables

#### 4.1.1 Body Mass Index

Body Mass Index (BMI) = Body weight in kilograms divided by the square of the height in meters.

### 4.2 Primary Endpoint Definition

Change in cerebral NAD/ATP- $\alpha$  ratio measured by 31 Phosphorus magnetic resonance spectroscopy ( $^{31}\text{P}$ -MRS) in the posterior brain (encompassing the occipital, parietooccipital and posterior parts of the temporal cortex). The variables are continuous.

The **primary analysis** of the **primary endpoint** will be:

- The comparison between the dose stable (DS-group) and dose escalation group (DS-group), in cerebral NAD levels measured by  $^{31}\text{P}$ -MRS at week 12 depending on randomization group and adjusted for  $^{31}\text{P}$ -MRS at baseline.

The **secondary analyses** of the **primary endpoint** will be:

- The comparison of change over time from baseline to week 4, week 8 and week 12, between the DE-group, PL-group and the DS-group, in cerebral NAD levels measured by  $^{31}\text{P}$ -MRS, depending on randomization group, time and their interaction adjusted for random individual intercept.
- The comparison between the dose stable (DS-group) and placebo group (PL-group), in cerebral NAD levels measured by  $^{31}\text{P}$ -MRS at week 12 depending on randomization group and adjusted for  $^{31}\text{P}$ -MRS at baseline.

### 4.3 Secondary Endpoint Definition

#### 4.3.1 Determine whether NR-therapy augments NAD levels in the central nervous system (CNS) in a dose-responsive manner, as measured by LC-MS

Change in the cerebrospinal fluid (CSF) levels of NAD or other metabolites of the NAD metabolome\*, measured. If NAD is measured directly this will be compared. If NAD is not detected or not measurable, the metabolite reflecting NAD levels, will be used for analysis. The variables are continuous. Metabolites from the NAD metabolome will be measured by liquid chromatography mass spectrometry. The variables are continuous.

The **primary analysis** of the **secondary endpoint** will be:

- The comparison between the dose stable (DS-group) and dose escalation group (DE-group), in NAD or NAD metabolite\* levels measured by HPLC-MS at week 12 depending on randomization group and adjusted for NAD or NAD metabolite\* at baseline.

The **secondary analysis** of the **secondary endpoint** will be:

- The comparison between the dose stable (DS-group) and placebo group (PL-group), in NAD or NAD metabolite\* levels measured by HPLC-MS at week 12 depending on randomization group and adjusted for NAD or NAD metabolite\* at baseline.

**\*The NAD metabolome is comprised of:** Nicotinamide adenine dinucleotide oxidized (NAD+), Nicotinamide adenine dinucleotide reduced (NADH), NAD+/NADH ratio, total NAD (sum of NAD+ and NADH), Nicotinamide adenine dinucleotide phosphate oxidized (NADP+), Nicotinamide adenine dinucleotide phosphate reduced (NADPH), NADP+/NADPH ratio, total NADP (sum of NADP+ and NADPH, 1-methyl nicotinamide (Me-Nam), nicotinic acid-adenine dinucleotide (NAAD), N1-methyl-2-pyridone-5-carboxamide (Me-2-PY), Nicotinamide (Nam), Nicotinamide N-oxide (Nam N-oxide), ADP-ribose (ADPR), Nicotinic acid riboside (NAR), Nicotinamide riboside (NR), Nicotinamide mononucleotide (NMN), Nicotinic acid (NA).

#### 4.4 Exploratory Endpoint Definitions

Due to the exploratory nature of the trial these outcomes are subject to change of analysis method. The preliminary plan for analysis is the following:

The following exploratory outcomes were recorded at V1, V2, V3 and V4 and will be analysed using the same methodology as the primary endpoint (see section 4.2):

- Change in the NR-related pattern (NRRP). This is calculated from the FDG-PET scans as described in the imaging protocol section of the trial protocol. The values are continuous variables.
- Change in the PD-related pattern (PDRP). This is calculated from the FDG-PET scans as described in the imaging protocol section of the trial protocol. The values are continuous variables.
- Change in the NAD metabolome in blood and urine as measured by HPLC-MS. These values are continuous variables.
- Change in motor symptoms from PD as measured by the MDS-UPDRS scale. The scale will be analysed both as total MDS-UPDRS scale, combined by subsections I-III and by subsections I-IV individually. The values are continuous variables.
- Change in non-motor symptoms from PD as measured by the mGIDS and MDS-NMS scales. Scales will be analysed both as total scores and by subsections. The values are continuous variables.
- Change in cognition as measured by the MoCA scale. Scales will be analysed both as total scores and by subsections. The values are continuous variables.
- Change in quality of life in PD, as measured by the EQ-5D-EL scale. Scales will be analysed both as total scores and by subsections. The values are continuous variables.
- Change in inflammatory markers in blood and/or urine. These values are continuous variables.
- Change in proteostasis, measured by RNA expression analysis of lysosomal and proteasomal pathways. These values are continuous variables.
- Change in gene and protein expression in PD. These values are continuous variables.

- Change in methylation metabolism via decreased availability of methyl-donors such as for example S-adenosyl methionine (SAM). These values are continuous variables.
- Change in methylation metabolism via decreased DNA methylation globally or at specific sites. These values are continuous variables.
- Change in methylation metabolism via decreased DNA methylation globally or at specific sites. These values are continuous variables.
- Change in methylation metabolism via aberrant folate and one-carbon metabolism. These values are continuous variables.

The following exploratory outcomes were recorded at V1 and V4 and will be analysed using the same methodology as the secondary endpoint assessing NAD in CSF (see section 4.3):

- Change in olfaction as measured by the B-SIT score. These values are continuous variables.
- Change in the NAD metabolome in the central nervous system as measured by HPLC-MS. These values are continuous variables.
- Change in inflammatory markers in the central nervous system. These values are continuous variables.
- Change in methylation metabolism via decreased synthesis of neurotransmitters like dopamine and serotonin. These values are continuous variables.
- Change in gut microbiome composition as measured by microbial DNA analysis of faeces. These values are continuous variables.

## 4.5 Overview of Endpoints

Endpoint level	Analysis level	Endpoint	Timeframe	Type
Primary Endpoint				
	Primary	Cerebral NAD  P-MRS: Difference between DE-group and DS-group.	84 ± 7 Days	Continuous
	Secondary	Cerebral NAD  P-MRS: Difference between DE-group-, DS-group, and PL-group.	84 ± 7 Days	Continuous
	Secondary	Cerebral NAD  P-MRS: Difference between DS-group and PL-group.	84 ± 7 Days	Continuous
Secondary Endpoint				
	Secondary	NAD levels in CSF: Difference between DE-group and DS-group.	84 ± 7 Days	Continuous

Secondary	NAD levels in CSF: Difference between DS-group and PL-group.	84 ± 7 Days	Continuous
-----------	--	-------------	------------

**Exploratory Endpoints (see section 4.4)**

---

**Safety**

N/A	Number and severity of adverse events between treatment groups and study visits.	During trial	Continuous
-----	--	--------------	------------

---

## 5 Analysis Methods

### 5.1 Methods for Primary Endpoint

#### 5.1.1 Descriptive Statistics

Cerebral NAD measured by P-MRS will be summarized by group for visits V1, V2, V3 and V4 using descriptive statistics (N, mean, standard deviation). Descriptive statistics will be based on non-imputed data. Data will be presented both in tabular and graphical format.

#### 5.1.2 Primary Inferential Analysis

The *primary analysis* of the *primary endpoint* will be performed using analysis of covariance (ANCOVA) between the dose stable (DS-group) and dose escalation group (DE-group), i.e. the regression of NAD levels measured by P-MRS at week 12 depending on randomization group and adjusted for P-MRS at baseline. No additional adjustments/covariates will be used. As this is the single primary outcome, alpha will be set at 0.05. No correction for multiple testing will be performed.

The formula for this calculation in R is:

```
lm_object = lm(NAD_at_V4 ~ Group + NAD_at_V1)
```

#### 5.1.3 Effect Estimates

The primary effect estimate will be the B-coefficient with confidence intervals and Cohen's d. Cohen's d will be calculated as the difference in the means between two groups and divided by the pooled standard deviation.

The Beta coefficient will be calculated in R in the following manner:

```
Beta_coffecient = summary(lm_object)$coefficients
```

Confidence intervals will be calculated in R in the following manner:

```
Confidence_intervals = confint(lm_object)
```

P-values will be retrieved from the summary of the lm\_object:

```
P_values = summary(lm_object)$coefficients
```

#### 5.1.4 Assumption Checks and Alternative Analyses

Assumptions for ANCOVA will be tested in the following manner:

Normal distribution of residuals: Normality of residuals will be assessed by QQ-plots and the Shapiro-Wilk test.

#### 5.1.5 Missing Data

For the primary outcome, missing data occur if a patient has not completed the study or not completed P-MRS imaging within the time window of the final visit 12 weeks  $\pm$  7 days.

As the primary analysis uses two timepoints (V1 and V4), in the case of a participant missing V4 measurements, this patient will not be included in the analysis.

For the secondary analysis of the primary outcome using a linear mixed model (LME, see point 5.1.7), missing data will not be imputed but treated as missing at random.

### 5.1.6 Sensitivity Analyses

Sensitivity analysis will be performed by comparing the results of analysis with the FAS and PPS populations. If there is a notable difference this will be commented upon.

### 5.1.7 Secondary Analyses of the Primary Endpoint

The *secondary analyses* of the *primary endpoint* will be:

1. Analysis of covariance (ANCOVA) between the dose stable (DS-group) and placebo group (PL-group), i.e. the regression of NAD levels measured by P-MRS at week 12 depending on randomization group and adjusted for P-MRS at baseline. No additional adjustments/covariates will be used. No correction for multiple testing will be performed.

The above-mentioned analysis will be performed in the same manner as the primary analysis for the primary endpoint.

2. Comparison of change over time from baseline to week 4, week 8 and week 12, between the DE-group, DS-group and the PL-group. This will be assessed using a linear mixed model (LME), i.e. NAD (P-MRS) at weeks 4, 8 and 12 depending on randomization group, time and their interaction adjusted for random individual intercept. The above-mentioned analysis will be performed using a linear mixed model (LME) comparing NAD level as a function of group with time and the interaction between group and time as independent variables. Individual subjects will be random effects.

The following formula will be used in R format:

```
NAD_level ~ Group + Visit + Group * Visit + (1 | Subject)
```

Visit will be treated as a numeric variable if there is no plateau effect. If there is a plateau effect in the data, visit will be treated as a factor.

The primary effect estimate will be the B-coefficient with confidence intervals and Cohen's d. Cohen's d will be calculated as the difference in the means between two groups and divided by the pooled standard deviation.

The dose stable group will be set as the reference to which the dose escalation and placebo groups will be compared.

No additional covariates will be included in the LME model.

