## 10.4 Planned analyses

All statistical analyses will take place after the completion of the study. All randomized patients will be included in the primary analyses and sensitivity analyses will be carried out comparing results from the ITT, SAS and PPS data sets. In the case of missing assessments, the subject will be included if possible.

The **primary analysis** of the primary endpoint will be performed using analysis of covariance (ANCOVA) between the dose stable (DS-group) and dose escalation group (DS-group), i.e. the regression of NAD levels measured by  $^{31}\text{P}$ -MRS at week 12 depending on randomization group and adjusted for  $^{31}\text{P}$ -MRS at baseline. No additional adjustments/covariates will be used. As this is the single primary outcome, alpha will be set at 0.05. No correction for multiple testing will be performed.

The **secondary analysis** of the primary endpoint will be the comparison of change over time from baseline to week 4, week 8 and week 12, between the DE-group and the DS-group. This will be assessed using a linear mixed model (LME), i.e. NAD ( $^{31}\text{P}$ -MRS) at weeks 4,8 and 12 depending on randomization group, time and their interaction adjusted for random individual intercept.

The **primary analysis** of the secondary endpoint will be performed using ANCOVA between the dose stable (DS-group) and dose escalation group (DS-group), i.e. the regression of NAD or NAD metabolite levels measured by HPLC-MS at week 12 depending on randomization group and adjusted for NAD or NAD metabolite at baseline. No additional adjustments/covariates will be used.

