#### 1.3.2 Secondary Objectives

The secondary objectives of this study are to:

- Assess the dose-response relationship between NR dose (1000 mg, 2000 mg, 3000 mg per day) and changes in cerebral NAD levels from baseline to weeks 4, 8 and 12.

- Compare the effectiveness of orally administered nicotinamide riboside (NR) 1500 mg twice per day versus 500 mg twice per day in augmenting the NAD-metabolome in the central nervous system (CNS) at week 12.

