### 5.3 Methods for Continuous Exploratory Endpoints

As described in section 4.4, due to the nature of the exploratory outcomes, the analysis method is subject to change. The preliminary plan is that they will be analysed in the same manner as the primary endpoint if they have observations at V1, V2, V3 and V4 (see sections 5.1.2 and 5.1.7) and the same manner as the secondary endpoint if they only have observations at V1 and V4 (see sections 5.2.2 and 5.2.7).

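### The mixed-model text conflicts on whether baseline NAD is used; read literally, the model does not estimate change from baseline, and a stable 1000 mg effect has expectation zero in the DS-versus-placebo interaction

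*SAP*

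**What the plan says.** The secondary objective in SAP 1.3.2 concerns "changes in cerebral NAD levels from baseline to weeks 4, 8 and 12", by NR dose. SAP 5.1.7 item 2 gives the matching analysis: "Comparison of change over time from baseline to week 4, week 8 and week 12, between the DE-group, DS-group and the PL-group". It then specifies a linear mixed model whose response is NAD "at weeks 4, 8 and 12 depending on randomization group, time and their interaction adjusted for random individual intercept". The R formula is "NAD_level ~ Group + Visit + Group * Visit + (1 | Subject" plus its closing bracket, with no baseline term and no list of Visit levels. The section adds: "No additional covariates will be included in the LME model". On coding, "Visit will be treated as a numeric variable if there is no plateau effect"; otherwise it becomes a factor. DS is the reference group. The effect estimate is called the B-coefficient, without saying which one.

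Protocol 10.4 describes the response in almost the same words ("at weeks 4,8 and 12 depending on randomization group, time and their interaction adjusted for random individual intercept"), for DE versus DS only. It lists no baseline term for this model.

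Other sections point the other way. SAP 4.2 defines the same comparison from baseline and does not limit the response to the three post-baseline visits. SAP 2.4 lists V1 as an analysis time point. SAP 4.4 and 5.3 send the repeatedly measured exploratory endpoints to this method: "they will be analysed in the same manner as the primary endpoint if they have observations at V1, V2, V3 and V4".

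Item 1 of SAP 5.1.7 separately plans a DS-versus-placebo ANCOVA at week 12, adjusted for baseline.

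**The concern.** The sentence that defines the model leaves V1 out of the response, and the bar on covariates keeps it off the right-hand side. Group is then an on-treatment difference unadjusted for baseline, and Group x Visit is change since week 4. Neither is the stated target. The DS arm takes the same dose from day 0, so an effect complete by week 4 cannot appear in a DS-versus-placebo term that starts counting at week 4.

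At stake is what a named secondary analysis reports. Two programmers following the same SAP could obtain an expected 0 or an expected 0.27 for the same comparison. This is also the only planned model that uses the week 4 and week 8 NAD data, and SAP 5.3 carries it to NRRP, PDRP, MDS-UPDRS and the other endpoints measured at all four visits.

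**Working it through.** The plan gives no figure for the mixed model, so there is none to reproduce. Its one sample-size figure (30 in DE, raised to 40) does not bear on this point.

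**Inputs from the documents**
- 1000 mg multiplies cerebral NAD by 1.27, read as +0.27 of baseline; placebo change is negligible (SAP 5.5; -0.43%, taken as 0).
- The response is linear in dose (SAP 5.5): +0.27, +0.54, +0.81.
- NAD reaches a plateau within 1-2 weeks of treatment (Protocol 10.3, footnote).
- Arms are PL 20, DS 20, DE 40.

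**Assumed:** visit correlation rho, and an SD of change of 0.38. The SD is back-calculated from the earlier trial's paired P = 0.016 with n = 15: t = 2.739, t/sqrt(15) = 0.707, 0.27/0.707 = 0.38.

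**Step 1. Expected profiles at V1, V2, V3, V4**
- PL: 0, 0, 0, 0
- DS: 0, 0.27, 0.27, 0.27
- DE: 0, 0.27, 0.54, 0.81

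**Step 2. Expected interactions.** The factor term is the last difference minus the first. The numeric term is the slope, sum of (x - mean x) times the difference, divided by sum of (x - mean x) squared.

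| Response rows | Contrast | Differences | Factor, week 12 | Numeric slope per visit |
|---|---|---|---|---|
| V2-V4 | DS-PL | 0.27, 0.27, 0.27 | 0.27 - 0.27 = **0** | (-0.27 + 0.27)/2 = **0** |
| V2-V4 | DE-DS | 0, 0.27, 0.54 | 0.54 | (0 + 0.54)/2 = 0.27 |
| V1-V4 | DS-PL | 0, 0.27, 0.27, 0.27 | **0.27** | 0.405/5 = 0.081 |
| V1-V4 | DE-DS | 0, 0, 0.27, 0.54 | 0.54 | 0.945/5 = 0.189 |

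Without V1, the DS-PL difference of 0.27 moves to the Group term. With V1 and numeric coding, the 0.27 step is fitted as 3 x 0.081 = 0.243. None of these expectations depends on the assumed SD or rho.

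**Step 3. Rejection rates** (4000 simulated trials per setting, 20/20/40, random intercept, rho 0.3, 0.5 and 0.7, two-sided 5%)
- DS-PL interaction, V1 out: 5%, which is alpha.
- DS-PL interaction, V1 in: about 60% (factor) or 55% (numeric).
- DS-PL Group term, V1 out: about 75%, 60% and 42% as rho rises.
- DS-PL ANCOVA at week 12: about 76%, 70% and 65%.
- DE-DS interaction (numeric Visit), either way: over 99%.

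**Step 4. Precision.** In units of the single-visit variance, the variance of an arm difference is proportional to 1 when baseline is ignored, to 2(1 - rho) for change from an unconstrained V1, and to 1 - rho^2 when adjusted for baseline. Relative to adjustment:
- baseline ignored: 1/(1 - rho^2) = 1.33 at rho 0.5 and 1.96 at rho 0.7. This applies to a difference at one visit, not to the within-subject interaction.
- V1 as unconstrained outcome: 2(1 - rho)/(1 - rho^2) = 2/(1 + rho) = 1.33 and 1.18.

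**The case against.** The best defence is that V1 was always meant to be in the model. Neither document says that the response is restricted to the three later visits alone. The stated aim is change from baseline, the formula restricts no rows, and SAP 4.2, 4.4 and 5.3 all fit V1 as a Visit level. With Visit as a factor, Group x Visit is then exactly change from baseline. This stands in part: exclusion of baseline is one reading and not a settled fact. It does not remove the conflict, because the defining sentence appears in both documents and the SAP elsewhere names V1 when it wants it.

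A reader might infer more than the text supports:
- *That the 1000 mg effect would be missed.* No. Item 1 of SAP 5.1.7 estimates it with baseline adjustment, and the Group term carries it even without V1.
- *That the dose-response objective fails.* No. Both NR arms take 1000 mg up to week 4, so the DE-DS interaction survives. Placebo is not among the doses in that objective.
- *That the interaction is zero whatever the time course.* No. The effect must be complete and flat by week 4. The Protocol 10.3 footnote suggests this for NAD, without naming cerebral NAD. Nothing shows it for NRRP, PDRP or the clinical scales, whose methods SAP 4.4 and 5.3 call preliminary.

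It may also be said that an unconstrained V1-V4 model is valid under randomisation. It is, and the precision argument against it rests on an assumed rho.

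**Conclusion.** The point holds as an unresolved conflict with a definite consequence under the literal reading. On that reading, SAP 5.1.7 item 2 does not estimate the change from baseline that it names, and the DS-PL interaction has expectation 0 where the true difference in change is 0.27. That size rests on the plan's own effect, complete and stable by week 4. On the other reading the target is right, but the estimate has 2/(1 + rho) times the variance of a baseline-adjusted one.

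Two features make the gap worse: no coefficient is named as the result, and the choice between numeric and factor Visit depends on a plateau seen in the data, whose appearance itself depends on whether V1 is included. The power figures depend on an assumed SD and rho and are indicative only.

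This is a should-fix for a secondary analysis.

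**What to change.** Rewrite SAP 5.1.7 item 2 and the matching paragraph of Protocol 10.4:
- Choose one form. Either outcomes at V2-V4 with V1 NAD and V1 x Visit as covariates, or outcomes at V1-V4 with arm means constrained equal at V1.
- Prespecify Visit as a factor and drop the plateau rule.
- Name the contrasts: baseline-adjusted DE-DS at weeks 8 and 12, and DS-PL averaged over weeks 4 to 12.
- Amend the bar on covariates to allow the baseline term.
- State the same form in SAP 5.3, using each endpoint's own V1 value.

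The cost is SAP and protocol wording and a few lines of R. V1 is already collected, so no new data are needed. The SAP is dated 16 June 2025, after the estimated last-patient date of 22 April 2025, so the choice should be recorded before the model is run.
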